**Table 7: EAP SHH4811g Overall Response (RECIST) at Study Termination**

	laBCC (n=56)	mBCC (n=39)
Objective response, n (%)	26 (46.4)	12 (30.8)
(95% CI)	(32.4-59.3)	(17.0-47.6)
Complete response, n (%)	6 (10.7)	2 (5.1)
Partial response, n (%)	20 (35.7)	10 (25.6)
Stable disease, n (%)	27 (48.2)	20 (51.3)
Progressive disease, n (%)	0	3 (7.7)
Unevaluable/missing, n (%)	3 (5.4)	4 (10.3)
Median time to response (range), months a	2.6 (1.0-11.0)	2.6 (1.4-12.6)

**Table 8: SHH4811g Vismodegib Expanded Access Study Common Treatment-Emergent Adverse Events**

TEAEs (n=120)	Median Time to AE Onset, Days (95% CI)*	All AEs, n (%)	Gr 1, n (%)	Gr 2, n (%)	Gr 3, n (%)	Gr 4, n (%)	Gr 5, n (%)
Muscle spasms	37 (28-44)	84 (70.0)	63 (52.5)	19 (15.8)	2 (1.7)	–	–
Dysgeusia	41 (30-51)	84 (70.0)	68 (56.7)	16 (13.3)	n/a	n/a	n/a
Alopecia	87 (74-104)	69 (57.5)	57 (47.5)	12 (10.0)	n/a	n/a	n/a
Diarrhea	38 (22-116)	30 (25.0)	23 (19.2)	5 (4.2)	1 (0.8)	1 (0.8)	–
Nausea	30 (11-130)	23 (19.2)	19 (15.8)	4 (3.3)	–	–	–
Fatigue	42 (16-120)	23 (19.2)	14 (11.7)	8 (6.7)	1 (0.8)	–	–
Weight decreased	175 (114-293)	19 (15.8)	12 (10.0)	7 (5.8)	–	–	–

\*For those patients experiencing the TEAE

## Phase II BCNS Study (SHH4685s)

The anti-BCC efficacy of vismodegib was tested in a randomized, double-blinded, placebo-controlled, Investigator-sponsored trial in Gorlin syndrome (BCNS) patients with surgically eligible BCCs (Tang et al. 2012). Forty-one patients were randomized 2:1 to receive oral vismodegib (n=26) or placebo (n=15). After a mean follow up of 8 months (range, 1 to 15 months), the per-patient rate of new surgically eligible BCCs (SEBs) was lower with vismodegib than with placebo (2 vs. 29 cases per group per year,  $p<0.001$ ), as was the size (percent change from baseline in the sum of the longest diameter) of existing clinically significant BCCs ( $-65\%$  vs.  $-11\%$ ,  $p=0.003$ ). In some patients, all BCCs clinically regressed. No tumors progressed during treatment with vismodegib. Patients receiving vismodegib routinely had Grade 1 or 2 AEs of loss of taste, muscle cramps, hair loss, and weight loss. Overall, 54% of patients (14 of 26) receiving vismodegib discontinued drug treatment due to AEs. At 1 month, vismodegib use had reduced the Hh pathway's target-gene expression in BCC cells by 90% ( $p<0.001$ ) and diminished tumor-cell proliferation, but apoptosis was not affected. No residual BCC was detectable in 83% of biopsy samples taken from sites of clinically regressed BCCs. At the second pre-specified interim analysis, a data safety and monitoring board concluded that the pre-determined threshold for a significant difference between the two groups had been reached ( $p<0.0113$ ), and the treatment with placebo in this arm was terminated. See the Vismodegib Investigator Brochure and the US package insert for additional details on nonclinical and clinical studies on vismodegib.

**Table 9: Phase II BCNS Study (SHH4685s) Adverse Events Reported in  $\geq 10\%$  of Patients**

Grade 1 or 2 AEs, n (%)	Vismodegib (n=26)	Placebo (n=15)	P Value
Taste disturbance, n	22 (85)	1 (7)	<0.001
Muscle cramps	21 (81)	0 (0)	<0.001
Hair loss	16 (62)	1 (7)	0.004
>5% weight decrease	11 (42)	0 (0)	0.003
GI upset	5 (19)	1 (7)	0.14
Acne	3 (12)	1 (7)	0.60

## **Phase II STEVIE (MO25616) Safety Study**

Study MO25616 is an ongoing Phase II open-label, single-arm, multicenter (ex-U.S.) study of vismodegib in patients with locally aBCC or mBCC who are otherwise without satisfactory treatment options. The primary objective is to assess the safety of vismodegib in patients with locally aBCC or mBCC. Secondary objectives are to assess the overall response (according to RECIST Version 1.1) in those patients with measurable disease as permitted by local regulatory requirement and to assess other efficacy parameters such as time to response, duration of response, PFS, and overall survival (OS).

All patients receive 150 mg vismodegib orally (PO) daily (QD) until investigator-assessed progression of disease (PD), unmanageable toxicities, or withdrawal from study (investigator/patient request).

As of 6 November 2013, a total of 1228 patients have been enrolled into the study. Results of an interim analysis, when a total of 501 patients could be followed for 1 year, are presented below.

As of the cutoff date of 6 November 2013, safety data were available for 500 patients (469 with locally aBCC and 31 with mBCC) with followup information for at least 3 months after treatment. Overall, 492 of 500 safety-evaluable patients (98.4%) experienced at least one AE. The most frequently reported AEs, regardless of relationship to study drug, in descending order of frequency, were: muscle spasms (63.2%), alopecia (61.0%), dysgeusia (53.8%), weight decreased (32.4%), asthenia (28.2%), decreased appetite (25.4%), and ageusia (22.4%).

As of 6 November 2013, 210 of 500 safety-evaluable patients (42.0%) experienced Grade 3–5 treatment-emergent adverse events (TEAEs). Of 500 patients, 165 patients (33.0%) experienced a Grade 3 AE, 24 patients (4.8%) experienced a Grade 4 AE, and 21 patients (4.2%) experienced a Grade 5 AE. All of the Grade 5 AEs were considered by investigator to be unrelated to treatment with vismodegib except for cardio-respiratory arrest and myocardial infarction.

Of the 500 patients, 107 (21.4%) experienced SAEs. The most common events were in the following system organ classes: infections and infestations, 30 patients (6.0%); neoplasms (benign, malignant, and unspecified, including cysts and polyps), 16 patients (3.2%); general disorders and administration site conditions, 12 patients (2.4%); nervous system disorders, 12 patients (2.4%); cardiac disorders, 11 patients (2.2%); injury, poisoning and procedural complications, 10 patients (2.0%); and metabolism and nutrition disorders, 10 patients (2.0%).

As of 6 November 2013, there have been 29 deaths among 500 safety-evaluable patients. The causes of death were PD in 4 patients, AE in 20 patients, and 5 patients with “other” as cause of death. Most patient deaths were considered unrelated to treatment with vismodegib. Two

deaths (cardiopulmonary arrest and cardiac infarction) were assessed by the investigator as related to vismodegib; however, both patients had significant risk factors and comorbidities. Both events were considered by the investigator to be related because of the temporal relationship between the onset of the event and administration of vismodegib; therefore, an association could not be excluded.

As of 6 November 2013, 400 of 500 patients (80%) treated during Study MO25616 had discontinued study drug. Reasons for discontinuation of study drug included: AE (178 patients, 35.6%); progression of disease (70 patients, 14.0%); patient request (62 patients, 12.4%); death (10 patients, 2.8%); investigator request (14 patients, 2.8%); lost to follow-up (4 patients, 0.8%); and other (62 patients, 12.4%).

The majority of patients (98.2%) in Study MO25616 (STEVIE) experienced TEAEs. The most common (>20%) TEAEs included muscle spasm (63.2%), alopecia (61.0%), dysgeusia (53.8%), weight decreased (32.4%), asthenia (28.2%), decreased appetite (25.4%), and ageusia (22.4%). Twenty-four (4.8%) Grade 4 events and 21 (4.2%) Grade 5 events were reported. Two of the deaths were considered related to vismodegib treatment (cardio-respiratory arrest and myocardial infarction). There were 107 (21.4%) patients who reported SAEs. Common SAEs that were reported in  $\geq 1\%$  of patients were pneumonia (1.8%, n=9), general physical health deterioration (1.4%, n=7), and dehydration (1.0%, n=5).

Interim results of the STEVIE study demonstrate that vismodegib is generally well tolerated in a patient population that is representative of patients treated in routine clinical practice, with a safety profile consistent with that previously observed in other vismodegib studies. Investigator-assessed response rates are consistent with those reported in the ERIVANCE study and confirm high rates of tumor control.

As the trial is ongoing, efficacy analyses will be presented at final analysis.

### **Phase II Operable Basal Cell Carcinoma (SHH4812g) Study**

The ability of vismodegib to induce complete histological clearance (CHC) of BCC tumors, an important step in assessing the role of the drug in the setting of smaller resectable lesions, was examined in a single-arm, 3-cohort, Phase II study (Sofen et al. 2015). Patients in the trial were required to have one clinically operable, nodular BCC lesion on the scalp (0.5 - 2.0 cm maximum diameter) or in the "cape" area (chest, shoulders, or upper back; 1.0 - 3.0 cm maximum diameter). The nodular BCC required a positive biopsy that was limited to  $\leq 25\%$  of the target lesion. After 12 weeks of oral vismodegib (150 mg QD), patients were assessed clinically and then underwent excision of the target tumor site for pathologic assessment of residual carcinoma, followed by re-excision of the tumor site for margin assessment using standard Mohs techniques.

Efficacy objectives for CHC were not met in this study. The CHC rates were 42% (10/24) in Cohort 1, 16% (4/25) in Cohort 2, and 44% (11/25) in Cohort 3; these clearance rates were not statistically significant (p-values of 0.8463, 0.9668, and 0.7878, respectively). The low response rate in Cohort 2 (4 [16%] of 25 patients) indicates a lack of durable response. Investigator-assessed clinical response (CR and PR) did not correlate with CHC. Time to complete clinical clearance in patients in Cohorts 1 (10 patients), 2 (9 patients), and 3 (18 patients) with investigator-assessed CR, the time to first CR was 59.5 days (95% CI: 28.0 □ 80.0 days), 84.0 days (95% CI: 27.0 □ 120.0 days), and 60.0 days (95% CI: 55.0 □ 86.0 days), respectively.

No new safety signals were noted for patients in this study after dosing with vismodegib 150 mg QD PO. No deaths occurred during this study. The safety profile of vismodegib 150 mg QD was similar among the 3 cohorts. The data generally showed reversibility of muscle spasms, dysgeusia, and ageusia 6 to 12 weeks after drug discontinuation, and reversibility of delayed-onset alopecia in most patients during the 24-week follow-up period in Cohort 2.

Efficacy objectives for CHC were not met in this study.

#### **1.3.1.2 Medulloblastoma**

Data from a phase II clinical trial evaluated vismodegib treatment at 150 mg QD in adult patients with medulloblastoma that was recurrent after or progressive while receiving standard care (n=40) [Gajjar et al 2013, Asklund et al 2013]. Patients were stratified by histologic subtypes based on immunohistochemical (IHC) analysis into three strata: non-SHH group, SHH group, and indeterminate group. The primary endpoint was objective response rate as assessed by RECIST using independent review. Responses must be sustained at least 8 weeks. The study met its primary endpoint of sustained objective response, with 3/20 patients in SHH group exhibiting sustained responses. Secondary efficacy endpoints were consistent with the primary endpoint. Grade 3-4 TEAEs reported were lymphocytopenia, thromboembolic event, syncope, back pain, myalgia, seizure, and hypophosphatemia.

### **1.3.2 Malignancies with Ligand Driven Hh Signaling**

#### **1.3.2.1 Colorectal Cancer**

A randomized phase II clinical trial evaluated addition of vismodegib or placebo to standard chemotherapy (mFOLFOX-6 or FOLFIRI) plus bevacizumab in patients with untreated metastatic colorectal cancer (n=199; Berlin et al 2013). Choice of chemotherapy regimen was based on investigator decision. The primary endpoint was improvement in progression-free survival (PFS). The study failed to meet its primary

endpoint of improved PFS vs. chemotherapy + placebo (hazard ratio 1.25 [90% CI 0.89 -1.76], p =0.28) Secondary efficacy endpoints were consistent with the primary endpoint. The TEAEs (all grades) that differed in frequency by 10% or more vs. placebo were vomiting, asthenia, weight loss, decreased appetite, dehydration, muscle spasms, and dysgeusia. Grade 3-5 TEAEs that differed in frequency by 5% or more vs. placebo were fatigue, nausea, asthenia, mucositis, peripheral sensory neuropathy, weight loss, decreased appetite, and dehydration.

### **1.3.2.2 Ovarian Cancer**

A randomized phase II clinical trial evaluated the use of vismodegib or placebo as maintenance treatment for patients with ovarian cancer in second or third complete remission (n=104; Kaye et al 2012). The primary endpoint was improvement of PFS. The study failed to meet its primary endpoint of improved PFS vs. placebo (hazard ratio 0.79 95% CI 0.46-1.35, p=0.39). TEAEs occurring in greater than 10% of vismodegib treated patients were dysgeusia/ageusia, muscle spasms, alopecia, nausea, fatigue, constipation, abdominal pain, decrease appetite, upper abdominal pain, arthralgia, vomiting and hypomagnesemia.

### **1.3.2.3 Pancreatic Cancer**

A randomized phase II clinical trial evaluated addition of vismodegib or placebo to standard chemotherapy (gemcitabine) in patients with untreated metastatic pancreatic cancer (n=106; Catenacci et al 2013). The primary endpoint was improvement in progression-free survival. The study failed to meet its primary endpoint of improved PFS vs. chemotherapy + placebo (HR = 0.81 95% CI 0.54 - 1.21, p=0.3) Secondary efficacy endpoints were consistent with the primary endpoint. The frequency of Grade 3/4 TEAEs reported vs. placebo (V/P) were neutropenia (32%/28%), hyponatremia (4%/15%), fatigue (13%/8%), hyperglycemia (23%/19%), elevated alanine aminotransferase (ALT; 13%/9%). TEAEs that differed in frequency by 10% or more vs. placebo were vomiting, asthenia, weight loss, decreased appetite and dehydration.

### **1.3.2.4 Glioblastoma Multiforme**

A phase II clinical trial evaluated vismodegib treatment at 150 mg QD in patients with glioblastoma multiforme that was recurrent after or progressive while receiving standard treatment (n=40; Sloan et al 2012). The primary endpoint was improvement in PFS at 6 months. The study failed to meet its primary endpoint of improved PFS at 6 months (median PFS 1.8 months 95% CI 1.40 - 1.9 months) Secondary efficacy endpoints were consistent with the primary endpoint. TEAE reported were abdominal infection, abdominal pain, atrial flutter, fatigue, hypophosphatemia, lymphocytopenia, and thrombocytopenia (1 patient each).

### **1.3.2.5 Gastric Cancer**

A randomized phase II clinical trial evaluated addition of vismodegib or placebo to chemotherapy (mFOLFOX-6) in patients with untreated metastatic gastric cancer (n=124;Cohen et al 2013). The primary endpoint was improvement in PFS. The study failed to meet its primary endpoint of improved PFS vs. chemotherapy + placebo (hazard ratio 1.03 95%CI 0.69 - 1.55, p=0.64) Secondary efficacy endpoints were consistent with the primary endpoint. No significant differences in the rates of common grade  $\frac{3}{4}$  TEAEs ( $\geq 5\%$  incidence) were observed between the vismodegib and placebo arms. The rates of grade  $\frac{1}{2}$  TEAEs were comparable with no significant differences except for a higher incidence of dysgeusia in the vismodegib arm (42%/16%, p=0.003).

### **1.3.2.6 Small Cell Lung Cancer**

A randomized phase II clinical trial evaluated addition of vismodegib or cixutumumab (IMC-A12) to standard chemotherapy (Cisplatin/Etoposide) in patients with untreated extensive stage SCLC (n=155;Belani et al 2013). The primary endpoint was improvement in PFS. The study failed to meet its primary endpoint of improved PFS vs. cisplatin/etoposide chemotherapy (hazard ratio 1.32, p=0.21) Secondary efficacy endpoints were consistent with the primary endpoint. Grade  $\frac{3}{4}$  TEAEs reported (chemotherapy alone vs. chemotherapy+vismodegib) included anemia (25%/ 9%), febrile neutropenia (15%/13%), neutropenia (48%/47%), thrombocytopenia (22%/6%), leukopenia (46%/41%), nausea (11%/11%), vomiting (9%/6%), hyperglycemia (2%/2%), muscle weakness (4%/0%), and renal dysfunction (6%/0%)

## **1.4 Background for Other Study Drugs**

There are no other study drugs.

## **2. STUDY OBJECTIVES**

### **2.1 Primary Objectives**

The primary goal of this project is to determine whether treatment with vismodegib of patients with locally advanced or recurrent orbital and/or periorbital BCCA will be associated with good ophthalmic outcomes, as measured using a novel Visual Assessment Weighted Score (Table 15). The primary objective emphasizes globe preservation and maintenance of visual acuity, and a score of 21 or greater (out of 50) will be considered a good outcome.

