# 1. INTRODUCTION

Basal cell carcinoma (BCCA) is the most common human cancer, and frequently affects facial structures. While rarely fatal, facial BCCA can be disfiguring and expensive to treat. Treatment of facial BCCA typically includes Mohs micrographic surgery followed by plastic reconstructive surgery. Success rates of treatment for non-metastatic BCCA that is limited to skin can approach 99%. However, deeply invasive BCCA can involve vital organs, such as the eye or lacrimal drainage system, requiring aggressive surgical interventions that often compromise organ function. Hence, there is a critical need for improved treatments of invasive BCCA in the face.

Vismodegib is a small, orally administrable molecule that functions as an antagonist of the smoothed receptor (SMO), which is part of the hedgehog signaling pathway. Vismodegib (Erivedge, Genentech), was recently approved by the Food and Drug Administration (FDA) for treatment of recurrent, locally advanced or metastatic BCCA. Its primary indication in these cases is organ preservation. Initial results from clinical usage have been very promising. However, it remains to be determined whether use of vismodegib in treating locally advanced periocular or orbital BCCA would increase the chance of preserving visual function. Furthermore, chronic use of vismodegib is associated with side effects, such as muscle spasms, weight loss, hair loss, fatigue, and loss of appetite. Some side effects, such as muscle spasms, can be functionally debilitating. Recent reports have suggested that vismodegib treatment for orbital BCCA may facilitate globe preservation even if surgery is eventually required (Kahana, Worden and Elner, JAMA Ophthalmol, 2013). **The goal of this study is to test whether treatment with vismodegib for periocular and orbital BCCA is associated with preservation of a functioning globe and lacrimal apparatus.** Recruitment will be limited to patients who meet the standard criteria for vismodegib treatment of locally advanced periocular/orbital BCCA, for whom vismodegib has the potential to be organ-preserving.

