### 3. STUDY PROTOCOL

#### 3.1 Description of the Study

In order to assess the potential of vismodegib to improve the vision- and lacrimal-related morbidities associated with orbital and periocular BCCA, this study will follow patients with globe-threatening orbital and lacrimal-threatening periocular BCCA treated with vismodegib as standard of care. The study will be prospective, open label, non-randomized, and will determine visual and lacrimal function of treated patients.

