#### **Basic Protocol (see flow chart at the end of the section):**

##### ***ELIGIBILITY AND ENROLLMENT***

- 1) Patients will be enrolled based on Eligibility Criteria, Section 4.1, at which time a pre-treatment visual assessment score will be obtained as a baseline (Table 14).
- 2) Enrollment will include Informed Consent and Baseline blood tests.
- 3) Enrollment will be performed by the PI, Co-I, or qualified designee.

**Table 14: Pre-treatment Visual Assessment Score:  
(This score provides a non-weighted baseline that will be used for testing the consistency and internal validity of the Post-treatment Visual Assessment Score (Secondary Objective #5).)**

VA in affected eye of at least 20/200	0/1
Ocular Motility intact	0/1
No diplopia	0/1
Binocularity (Fusion) +/- prism	0/1
Normal tear lake, No complaint of persistent tearing	0/1
Intact lacrimal system by probing/irrigation (both canaliculi to NLD)	0/1
Patient assessment of visual function on the affected side (Poor, Fair, Good)	0/1/2
Score Maximum	8

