**Table 15: Follow-up Visual Assessment Weighted Score:**

[figure not shown]
	Score (0=No; 1=Yes)	Max Weighted score
Intact globe (no enucleation or evisceration)	0/1	20
VA within 4 Snellen lines of baseline VA or better	0/1	5
VA at 20/200 or better	0/1	5
No binocular diplopia in primary gaze	0/1	2
Fusion (Fly) +/- prism	0/1	2
No symptomatic tearing	0/1	3
Intact lacrimal system by probing/irrigation (either canaliculus to NLD)	0/1	3
Patient pleased with visual function (Poor, Fair, Good)	0/1/2	5
Total possible:	9	50

Because there are no validated measures for assessing the success of treating orbital disease, a new, non-validated measure must be used. The Visual Assessment Weighted Score (VAWS) was developed for the purpose of this study. It is made up of standard ophthalmic exam points, as well as a subjective assessment of tearing and overall patient satisfaction. Because it is a composite score, weighting is used to emphasize visual acuity and an intact globe.

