### 3.2 Rationale for Study Design

**Hypothesis: Treatment of orbital and periocular BCCA with oral vismodegib facilitates globe-sparing treatment of orbital BCCA, and lacrimal apparatus-sparing treatment of medial canthal BCCA.**

This is a prospective study that will follow the interventional standard of care use of vismodegib in patients with locally advanced BCCA that threatens the globe or lacrimal drainage system (see flow chart), and utilize a laboratory approach to identify predictors of disease severity, progression and response to treatment.

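### A kept globe plus any one other item counts as success, so the primary test in practice measures globe retention and cannot by itself show preserved acuity or lacrimal function

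*Combined protocol and SAP*

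**What the plan says.** - **Success rule.** Section 2.1: "a score of 21 or greater (out of 50) will be considered a good outcome". The same sentence names two emphases of the primary objective: keeping the globe and keeping visual acuity (VA). The 21-point rule recurs in section 3.1 (Outcome Assessment, item 8), section 3.3, and section 4.9 (Analysis; Determination of Sample Size).
- **Weights.** The text under Table 15 says that "weighting is used to emphasize visual acuity and an intact globe". The table gives 20 points for an intact globe. The two VA items, "VA within 4 Snellen lines of baseline VA or better" and acuity of at least 20/200, carry 5 each. Absence of diplopia and fusion carry 2 each. Absence of tearing and the patency item, "Intact lacrimal system by probing/irrigation (either canaliculus to NLD"), carry 3 each. The rest is patient satisfaction.
- **Aims.** The Introduction sets the goal as testing for an association with "preservation of a functioning globe and lacrimal apparatus". Section 3.1 says that "this study will follow patients with globe-threatening orbital and lacrimal-threatening periocular BCCA". The section 3.2 hypothesis is that treatment "facilitates globe-sparing treatment of orbital BCCA, and lacrimal apparatus-sparing treatment of medial canthal BCCA".
- **Entry.** Section 4.1, item 4, separates orbital invasion or impending invasion (4a) from medial canthal tumour within 7 mm of the lacrimal apparatus (4b). Both groups enter the same primary test.
- **Components.** Section 2.2, objective 1, and section 4.9 examine the parts of the score as secondary outcomes. Neither gives a success definition, a denominator or an interval for them.
- **Baseline patency.** Table 14 records "Intact lacrimal system by probing/irrigation (both canaliculi to NLD"), which is stricter than the Table 15 item.

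**The concern.** The score is presented as a measure of ophthalmic outcome in which acuity counts alongside the globe. If the cut-off lies one point above the globe weight, the acuity and lacrimal items hardly affect who is classed as a success once the globe is kept. A positive primary result could then be read as evidence of preserved visual function, and for 4b patients of preserved lacrimal function, when the test has shown neither. For a 4b patient the lacrimal system is the structure that led to entry, and that patient can lose it and still count as a success.

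**Working it through.** **Inputs.** Weights from Table 15; cut-off 21 from section 2.1; n=50, null 30%, alternative 50% and one-sided 5% from section 4.9. The printed weights sum to 20+5+5+2+2+3+3+5 = 45. The stated total of 50 needs full satisfaction to be worth 10. Both readings were run: satisfaction 0/5/10 (total 50) and 0/2.5/5 (total 45).

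**Step 1: the plan's own power.** With P(X ≥ r) = Σ C(50,k) p^k (1−p)^(50−k) for k = r to 50, at p = 0.30:
- r = 20 gives 0.0848, which is too large.
- r = 21 gives 0.0478, so the test rejects at 21 or more successes.

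At p = 0.50, P(X ≥ 21) = 0.8987. The stated 90% power reproduces. (The 21 patients here and the 21-point cut-off are different quantities.)

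**Step 2: what the 21-point rule accepts when the globe is kept.** Score = 20 + the other items. The smallest non-zero amount from the others is 2, so any one item gives at least 22. Only the pattern with zero on everything else scores 20 and fails.

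| Globe kept and | Patterns | Successes |
|---|---|---|
| no restriction | 2^6 × 3 = 192 | 191 |
| both VA items failed | 2^4 × 3 = 48 | 47 |
| both lacrimal items (tearing, patency) failed | 48 | 47 |
| all four failed | 2^2 × 3 = 12 | 11 |

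The counts are the same on both readings. A patient who fails both lacrimal items can still score 50 − 6 = 44 (39 on the 45-point reading).

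**Step 3: globe removed.** If both VA items and fusion score 0, the maximum is 2+3+3+10 = 18 (13 on the 45-point reading), so no pattern succeeds. If VA and fusion points were credited to a removed eye, 33 of 192 patterns would reach 21 (7 on the 45-point reading). The Table 15 text gives no scoring rule for a removed eye.

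With the scoring of Step 3 stated, success and globe retention differ in one pattern only.

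**Step 4: consequence for the test.** Twenty-one patients, each with a kept globe and one minor item, give a positive result even if 0 of 50 meet either VA item. This is a logical possibility, not a forecast.

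**Step 5: would a higher cut-off guarantee acuity?** The highest globe-kept score with both VA items failed is 40, so the first cut-off that guarantees any VA item is 41. With the 4-line item failed the maximum is 45 (cut-off 46). With patency failed it is 47 (cut-off 48). On the 45-point reading the cut-offs are 36, 41 and 43.

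**Step 6: relation to a globe-and-acuity endpoint.** A patient with the globe intact and the 4-line item met scores at least 25. That rate therefore cannot exceed the rate of 21 or more.

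**The case against.** - **The emphasis on the globe is deliberate and disclosed.** This stands. The table is open about its weights, the score is described as new and non-validated, and its components are secondary outcomes. But section 2.1 names acuity in the same sentence as the globe, and disclosure does not change what a positive test shows.
- **Lacrimal function is not in the primary objective.** This also stands. A reader might infer that the primary test was meant to enforce lacrimal preservation and fails to. Section 2.1 does not name it and section 2.2 makes it secondary. What remains is that the Introduction and sections 3.1 and 3.2 state it as an aim, and the primary result cannot speak to it.
- **Pattern counts are not probabilities.** Correct. Acuity, fusion and satisfaction would be expected to move together, and the documents give no rates. The point rests on the scoring logic alone.
- **A higher cut-off would give acuity more influence.** Partly right. Among the 48 globe-kept patterns with both VA items failed, successes fall from 47 at 21 to 21 at a cut-off of 31 and 11 at 35 (7 and 1 on the 45-point reading). It gives no guarantee short of 41, and it would fail some patients whose acuity was kept.
- **Replacing the primary endpoint is costly.** This stands. It needs a null on the new definition, which the documents do not give. Against 30% with n=50, power is 89.9% at a true 50%, but 71.4% at 45% and 43.9% at 40%.

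**Conclusion.** The point holds, and it limits what the trial may conclude. The 21-point primary test is in practice a test of globe retention: 191 of 192 globe-kept patterns pass, and 47 of 48 do so with both VA items failed. It does not enforce the acuity emphasis of section 2.1, and it cannot support a claim of lacrimal preservation. This rests on the Table 15 weights and on scoring a removed eye 0 on VA and fusion. It does not depend on which total, 45 or 50, is intended.

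Three stronger readings are tempting but not supported:
- That the primary endpoint must be replaced. The test is coherent as a test of globe retention, its power reproduces, and the components are already to be examined.
- That enrolling 4b patients inflates the false-positive rate. That depends on globe-retention rates and a 4b share that the documents do not give.
- That the section 4.9 description of the 30% null as a rate of loss adds weight here. It is a separate question, and nothing above uses it.

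This should be fixed before analysis. It does not invalidate the test.

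**What to change.** Keep the 21-point primary test, its null and n=50.

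1. In sections 2.1, 3.3 and 4.9 (Analysis), state that a positive primary result supports a conclusion about globe retention only.
2. In section 4.9 (Analysis), prespecify two key secondary endpoints with exact 95% confidence intervals:
   - (a) The proportion of all enrollees with an intact globe and the 4-line VA item met. The 20/200 item alone would pass a fall from 20/20 to 20/200. Score a removed eye, or an eye with no sight, as 0 on both VA items and fusion; otherwise an eye without sight at baseline could pass the 4-line item.
   - (b) The proportion meeting the Table 15 patency item among criterion 4b patients patent at baseline. Record baseline patency on the either-canaliculus wording as well, since Table 14 asks for both.
3. Tabulate globe, VA and lacrimal results by criteria 4a and 4b. Base any statement about preserved acuity or lacrimal function on (a) and (b).

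Making (a) the primary endpoint is optional, and only if the sponsor can supply a null success rate on that definition and restate the power.

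**Cost.** The headline conclusion is narrower. One baseline field is added, from probing already done for Table 14, along with a few tables. VA is already part of the ophthalmic exam (Table 16, footnote 3). An eye without sight at baseline cannot succeed on (a) even if the globe is kept, and section 4.1 does not exclude such eyes. Subgroup rates will be imprecise: 10 of 15, with 15 an assumed subgroup size, has a Clopper-Pearson interval of 38% to 88%.
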